4 GENERAL ASPECTS FOR STATISTICAL ANALYSIS

4.1 Analysis populations

This section contains a description of analysis populations considered for analysis of data from adult subjects.

Data of pediatric subjects will be analyzed separately from data of adult subjects. Given the limited number of pediatric subjects expected to be enrolled, and as all pediatric subjects will be enrolled in an open-label caplacizumab arm, the data will be analyzed descriptively, and no comparisons can be made or inferential statistics performed.

4.1.1 *All screened subjects population*

All subjects who signed an informed consent form.

4.1.2 *Intent-to-treat population*

All subjects who were randomized. The intent-to-treat (ITT) population will be used for general outputs and for main efficacy analysis.

4.1.3 *Modified intent-to-treat population*

All randomized subjects who received at least 1 administration of study drug, as randomized (cfr. Section 4.3.5). The modified ITT (mITT) population will be used for selected (sensitivity) analysis of efficacy.

4.1.4 *Per protocol population*

The per protocol (PP) population is a subpopulation of the ITT population, excluding those subjects who have had a major protocol deviation.

4.1.5 *Safety population*

All subjects who received at least 1 administration of study drug, as treated (cfr. Section 4.3.5). The safety population will be used for analysis of safety, PK, PD, disease markers, and immunogenicity data.

4.1.6 *Open-label Caplacizumab population*

All subjects who received at least 1 administration of open-label study drug. The open-label Caplacizumab (OL Caplacizumab) population will be used in cases where a separate analysis of open-label period is performed.

4.2 General Methods

4.2.1 Calculation of descriptive statistics

For continuous parameters, descriptive statistics will be presented when $n \geq 2$. When $n=1$, only sample size (n) and mean, i.e. the value itself, are shown. Descriptive statistics will include the number of non-missing data points (n), the arithmetic mean, the standard deviation (SD) (for baseline summaries) or standard error (SE) (for post-baseline or change from baseline summaries), the median, minimum and maximum.

For categorical parameters, frequency tabulations are prepared, consisting of frequency counts (non-missing observations) and percentages.

Descriptive statistics of efficacy parameters will additionally include 95% confidence intervals (CI) as appropriate.

Descriptive statistics of PK concentrations and PD data will additionally include 5% and 95% percentiles, coefficient of variation (CV)% of arithmetic mean, geometric mean and geometric SD.

For the graphs showing mean values or percentages, an SE flag will be shown. For PK graphs showing geometric mean values, a geometric SD flag will be shown.

4.2.2 Calculation of percentages

Missing values will not be included in the denominator count when computing percentages.

4.2.3 Handling of values below (or above) a threshold

Values below (above) the detection limit will be imputed by the value of the detection limit itself, unless indicated otherwise. Listings will always present the original value. Example: if the database contains values like "<0.04", then for the descriptive statistics the value of the detection limit (0.04) shall be used. A value like ">1000" will be imputed by "1000". For categorization of values into discrete classes the original value will be considered if it is a boundary value (e.g. ADAMTS13 <10% will be considered for <10 category).

Individual PK concentrations below the limit of detection or below the quantification limit (BQL) will be reported as BQL. To compute descriptive statistics (i.e. mean (or median or geomean), SD, CV%, minimum and maximum), all BQL values will be treated as missing. When the total number of BQL values exceeds 1/3 of the total number of values at that time point, descriptive statistics should not be computed. Descriptive statistics not calculated for the above reasons should be reported as not calculated (NC).

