3.3.8. TREATMENT COMPLIANCE

To ensure treatment compliance, study drug will be administered by a health care professional (or under supervision of a health care professional in case of training for self-administration) during the hospital stay, except for ambulatory study drug administration.

For study drug administrations at the clinical site, the exact times of study drug administration will be recorded in the eCRF. If a dose is missed, the reason for the not-dosed IMP should be recorded in the eCRF. Compliance will be further confirmed by bioanalytical assessment of caplacizumab in plasma samples.

For ambulatory study drug administration, each subject will be provided with a patient diary to collect information (e.g., the timing, kit number, location of injection) of each study drug administration. For more information on the study patient diary, please refer to section [3.3.3](#).

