14.2.8 Exploratory analyses

14.3 Pharmacokinetics

Table 14.2.2.1: PK: Descriptive statistics of drug concentrations

Descriptive statistics of drug concentrations by scheduled sampling time and treatment group.
Population: safety population.

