The table will present a summary by treatment group and analysis period of (1) the number and percentage of subjects within each alternative NAb subject category, and (2) the number and percentage of subjects classified as pre-dose negative, pre-dose positive, TE negative and TE positive. Subject categories, treatment groups and analysis periods are given in Section 9.1.3.

Population: safety population.

Table 14.3.5.6: Immunogenicity: Incidence of drug-induced TE ADA status and pre-Ab status based on ADA and mADA assay results (overall subject classification) by hypersensitivity reaction

Table 14.3.5.3, repeated for each category of hypersensitivity reaction.

CONFIDENTIAL

Population: safety population.

Table 14.3.5.7: Immunogenicity: Incidence of drug-induced TE ADA status and pre-Ab status based on ADA and mADA assay results (overall subject classification) by treatment extension (Y/ N)

Table 14.3.5.3, repeated for each category of hypersensitivity reaction.

Population: safety population.

Table 14.3.5.8: Immunogenicity: Incidence of drug-induced TE ADA status and pre-Ab status based on ADA and mADA assay results (overall subject classification) by Rituximab use

Table 14.3.5.3, repeated for each category of hypersensitivity reaction.

Population: safety population.

Table 14.3.5.9: Immunogenicity: drug concentration by overall subject category (based on ADA/mADA assay results)

Descriptive statistics of drug concentrations by visit and by overall subject category for (1) Caplacizumab during DB period, (2) OL Caplacizumab (after Caplacizumab) during OL Caplacizumab period, and (3) OL Caplacizumab (after Placebo) during OL Caplacizumab period. Subject categories, treatment groups and analysis periods are given in Section 9.1.1.2.

Population: safety population

Table 14.3.5.10: Immunogenicity: RICO activity by overall subject category (based on ADA/mADA assay results)

Descriptive statistics of RICO activity by visit and by overall subject category for (1) Caplacizumab during DB period, (2) Placebo during DB period, (3) OL Caplacizumab (after Caplacizumab) during OL Caplacizumab period, and (4) OL Caplacizumab (after Placebo) during OL Caplacizumab period. Subject categories, treatment groups and analysis periods are given in Section 9.1.1.2.

Population: safety population

Table 14.3.5.11: Immunogenicity: Percent change from baseline in vWF:Ag concentration by overall subject category (based on ADA/mADA assay results)

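### Dropping BQL drug concentrations from the PK summaries, with no BQL count shown, biases on-treatment exposure upward and can mask a loss of exposure in the antibody-category tables

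*SAP*

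**What the plan says.** SAP 4.2.3 has two rules. The general one keeps values beyond a limit: "Values below (above) the detection limit will be imputed by the value of the detection limit itself, unless indicated otherwise". Drug concentrations get a different one. For the mean, median, geometric mean, SD, CV%, minimum and maximum, "all BQL values will be treated as missing". A suppression rule follows: "When the total number of BQL values exceeds 1/3 of the total number of values at that time point", the statistics are not computed and the cell reads NC. The SAP gives no reason for the difference.

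SAP 4.2.1 defines n as the count of non-missing points, and SAP 4.2.4 tabulates the frequency of missing values only for categorical variables. No table in the index counts BQL samples.

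The rule governs these outputs:
- Table 14.2.2.1 (SAP 14.3): "Descriptive statistics of drug concentrations by scheduled sampling time and treatment group".
- Table 14.3.5.9 (SAP 14.10): "Descriptive statistics of drug concentrations by visit and by overall subject category", where the category is the ADA/mADA classification.
- Tables 14.3.5.13 and 14.3.5.17: the same by NAb and alternative NAb category.

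SAP 9.2 says that immunogenicity data will be correlated with PK, PD and efficacy.

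**The concern.** A BQL result in a dosed subject is not missing at random. It is the low end of the distribution, so deleting it can only move location statistics up, and most where exposure is lowest. Because n then excludes the sample, the table reader cannot tell a sample measured as BQL from one never taken.

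BQL results on treatment are plausible. Under Protocol 3.4.11, samples during daily PE are taken before that day's PE and the s.c. dose is given after all other assessments, so most on-treatment samples are close to trough. Protocol 1.2.4 describes rapid renal clearance of unbound drug.

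The tables by antibody category are where this matters. If antibodies reduced exposure, the rule would shrink the displayed difference or replace the affected cell with NC.

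**Working it through.** The documents state no figure that depends on this rule, so there is nothing of the plan's own to reproduce.

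**Inputs from the documents:** the exclusion rule and one-third limit (SAP 4.2.3); 132 subjects randomized 1:1, so 66 per arm (SAP 3.1); treatment-emergent ADA in 9% of treated Phase II subjects (Protocol 1.2.4).

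**Assumptions:** concentrations at a time point are lognormal with CV 30%, 50% or 100%, and a fraction p falls below the limit, up to one third.

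**Step 1: bias within a cell.** Let s = sqrt(ln(1 + CV²)), and let q be the standard normal quantile at p. Reported value divided by true value:
- geometric mean: exp(s·φ(q)/(1 − p))
- arithmetic mean: Φ(s − q)/(1 − p)
- median: the reported median is the true percentile p + (1 − p)/2, so the ratio is exp(s·z) with z the normal quantile there.

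At p = 1/3, q = −0.431 and φ(q) = 0.3636. For CV 50%, s = sqrt(ln 1.25) = 0.472. Then:
- geometric mean: exp(0.472 × 0.3636/0.6667) = 1.294
- arithmetic mean: Φ(0.903)/0.6667 = 0.8168/0.6667 = 1.225
- median: exp(0.472 × 0.431) = 1.226

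| CV | BQL share | Geometric mean | Arithmetic mean | Median |
|---|---|---|---|---|
| 30% | 10% | 1.059 | 1.047 | 1.038 |
| 30% | one third | 1.174 | 1.148 | 1.135 |
| 50% | 10% | 1.096 | 1.067 | 1.061 |
| 50% | one third | 1.294 | 1.225 | 1.226 |
| 100% | 10% | 1.176 | 1.092 | 1.110 |
| 100% | one third | 1.575 | 1.345 | 1.431 |

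The reported median is the true 55th, 60th or 66.7th percentile at 10%, 20% or one third BQL. The reported minimum can never fall below the limit.

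**Step 2: bias between antibody categories.** Suppose antibody-positive subjects have a true geometric mean ratio r to antibody-negative subjects, and one third of the positives are BQL. The same limit sits at quantile q₂ = q + ln(r)/s in the negatives. Displayed ratio = r × exp(s·φ(q)/(1 − Φ(q))) ÷ exp(s·φ(q₂)/(1 − Φ(q₂))).
- CV 50%, r = 0.50: q₂ = −0.431 − 0.693/0.472 = −1.90, and the ratio is 0.50 × 1.294/1.033 = 0.63.
- Across CV 30% to 100%, a true 0.50 displays as 0.59 to 0.67, and a true 0.70 as 0.80 to 0.83.

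**Step 3: small cells.** 0.09 × 66 = 5.9, so take 6 antibody-positive subjects, for illustration only. SAP 4.2.3 counts against values at the time point and does not say whether that means the displayed cell or all groups together.
- Counted per cell: 2 of 6 is exactly one third, which does not exceed the limit, so two values vanish and n reads 4. Three or more give NC. If each sample had a 50% chance of being BQL, NC would appear with probability (20 + 15 + 6 + 1)/64 = 0.66.
- Counted across the 66 caplacizumab subjects: all 6 positives could be BQL, which is 6/66 = 9%, and the rule would not trigger. The row would be empty without an NC.

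**The case against.** The best defence is that the information survives elsewhere and nothing decisive depends on these tables.
- SAP 4.2.3 keeps original values in the listings, so Listing 16.2.4.1 shows every BQL result.
- RICO and vWF:Ag are tabulated by ADA/mADA category (Tables 14.3.5.10 and 14.3.5.11), by NAb category (14.3.5.14 and 14.3.5.15) and by alternative NAb category (14.3.5.18 and 14.3.5.19). The PK rule does not touch them.
- Figures 14.4.1.2, 14.4.1.8 and 14.4.1.11 are scatter plots of concentration by category, and Figure 14.4.1.22 plots each ADA-positive subject, although the SAP does not say how BQL values are drawn.
- A population PK/PD analysis has its own plan (SAP 8.3).
- Phase II antibodies showed no apparent influence on PK or PD (Protocol 1.2.4).
- For placebo and pre-dose Day 1 cells, where BQL is expected, NC does no harm.

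All of this stands and limits the severity. It does not repair the summary tables, where BQL and unsampled remain indistinguishable.

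Three stronger readings are tempting but not supported:
- A reader might infer that non-compliance is hidden. Protocol 3.3.8 does say "Compliance will be further confirmed by bioanalytical assessment of caplacizumab in plasma samples", but it names no summary table, and SAP 5.6 computes compliance as administrations received over planned.
- A reader might infer that an antibody effect could not be seen at all. The listings, scatter plots and RICO and vWF:Ag tables contradict that, and NC itself signals more than one third BQL.
- A reader might put the inflation of the mean at 1/(1 − p), or 1.50 at one third. That is an upper bound, reached only if every BQL value is truly zero.

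**Conclusion.** The point holds as a limitation of the PK concentration summaries. In on-treatment caplacizumab cells the bias is always upward. At the most the rule allows before NC, and under assumed CVs of 30% to 100%, it is 1.148 to 1.345 for the arithmetic mean and 1.174 to 1.575 for the geometric mean, with the true 66.7th percentile reported as the median. Differences between antibody categories are attenuated or suppressed in Tables 14.3.5.9, 14.3.5.13 and 14.3.5.17.

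The direction follows from the rule alone. The size rests on lognormality and on a CV and BQL rate that the documents do not give; if BQL is rare on treatment, the effect is negligible. The cell of about 6 is looser still, because the Phase II 9% is treatment-emergent ADA, whereas the tables split pre-existing and drug-induced antibodies. PK and immunogenicity are summarized descriptively, and no primary or key secondary test uses these values. This is a cheap improvement, not a threat to the trial's conclusions.

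**What to change.** Amend SAP 4.2.3 and the shells of the PK concentration tables:
1. Show n (%) BQL out of N sampled in every cell.
2. In on-treatment caplacizumab cells after the first dose, keep BQL values as the lowest ranks for the median and percentiles. Report the minimum as BQL where it applies, and the median as BQL if half or more are BQL. The median is then unbiased whenever fewer than half are BQL.
3. State that the one-third rule is counted per displayed cell and applies only to the mean, SD, CV% and geometric statistics. Print the BQL percentage beside NC.

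Keep the suppression. Removing it and substituting half the limit would print non-zero drug levels in placebo cells, and substituting zero leaves the geometric mean undefined.

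The cost is SAP wording, one extra column, and a mean and median handled differently, which needs a footnote. The mean and geometric mean stay biased below the one-third limit, but the BQL percentage beside them lets the reader judge by how much. No new data are needed.

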4.2.4 Handling of missing data

There is no imputation of missing values, unless specified otherwise. Frequency of missing values will be tabulated for categorical variables.

Handling of missing date (time) or partially known date (time) is described in Section [5.3](#) for time since TTP diagnosis and in Section [7.1.1](#) for adverse events.

4.2.5 Handling of outliers

There will be no outlier detection. All measured values will be included in the analyses.

4.2.6 Rounding of calculated parameters

Calculated parameters will not be rounded in the derived datasets. The rounding will be done at the reporting level.

4.3 Key Definitions and Labels

4.3.1 Definition of baseline

Baseline is defined as the last non-missing assessment before first administration of study drug.

For assessments with multiple parameters per subject (such as laboratory assessments), baseline will be determined per parameter individually. It is recognized that baseline assessments may thus come from more than one assessment and not just from the “baseline visit” assessment. Baseline will be calculated for each treatment period separately (double-blind treatment and open-label treatment). The assessment on Day 1 of the open-label treatment period, taken before first administration of open-label caplacizumab, will be taken as baseline value for the open-label part.

4.3.2 Change from baseline and percentage change from baseline

The change from baseline will be calculated for all post-baseline time points as:

Change from baseline at time point t = value at time point t – baseline value.

Percentage change from baseline at time point t = $100 * ((\text{value at time point t} - \text{baseline value}) / \text{baseline value})$.

Change from baseline and percentage change from baseline will be calculated separately for each of the treatment periods from their respective baseline values.

4.3.3 Handling of unscheduled assessments

Pre-dose unscheduled measurements: the latest non-missing pre-dose unscheduled measurement may be used for the possible imputation of a missing baseline (see Section 4.3.1). In all other cases, the value will only be listed.

Post-dose unscheduled measurements: the original scheduled measurement will be used for the analysis tables. Unscheduled samples will not be used in the descriptive statistics, but will be shown in listings.

Unscheduled measurements will be taken into account for derivation of time to event parameters and area under the curve (AUC). They will also be used if there is a worst-case determination over a period of time.

4.3.4 Screening and follow-up visits

For analyses by visit, screening visits will be shown for each treatment group, not pooled. For subjects who have not switched to open-label caplacizumab after recurrence, follow-up visits will be shown for each treatment group, not pooled. For subjects who have switched to open-label caplacizumab after recurrence, follow-up visits will be shown pooled for subjects who received caplacizumab during the double-blind treatment period and for subjects who received placebo during the double-blind treatment period. See Section 4.3.6. for more details.

4.3.5 Randomized versus actual treatment

Analyses will be handled differently before and after switch to open-label caplacizumab after recurrence, as specified below.

Before switch to open-label caplacizumab the treatment group as assigned by the randomization will be used (i.e., as-randomized analysis) for efficacy. For safety, PK, PD, disease-related markers and immunogenicity analyses the treatment that was actually used by the subject will be applied (i.e., as-treated analysis).

Differences between as-treated and as-randomized will be flagged in the listing on subject allocation.

After switch to open-label caplacizumab an all-treated analysis will be conducted in a separate pooled open-label caplacizumab treatment group, unless specified otherwise. For some specific analyses, e.g. for immunogenicity analyses; see Section 9.1, this pooling is not done. As a consequence, if open label period is represented according to the randomized treatment, the actual treatment (Caplacizumab) can differ from represented treatment group (Placebo or Caplacizumab).

4.3.6 Presentation of treatment groups

The following treatment group labels will be used in the tables, listings and figures, unless specified otherwise:

- Caplacizumab
- Placebo
- Open-label (OL) Caplacizumab

Treatment groups Caplacizumab and Placebo refer to the initial treatment group prior to a potential switch to open-label caplacizumab, and only data up to the switch are used in the analyses of these treatment groups. The OL Caplacizumab treatment group will only be used for analyses after the switch to open-label caplacizumab.

4.3.7 Totals over groups

Grand total, pooling all subjects, will be displayed in the tables on general characteristics.

4.3.8 General presentation of results

All results will be presented per treatment group, unless specified otherwise.

All listings will be ordered by treatment group, subject, and time point, unless specified otherwise.

The analysis population will always be indicated in a subtitle in the table, listing or figure.

4.4 Analysis Periods and Visit Windows

4.4.1 Analysis periods

The following analysis phases are defined for this study: Screening, Treatment, Follow-up. Within these analysis phases, the following analysis periods and subperiods will be considered:

Table 1: Analysis periods

Period	Subperiod	Start period	End period
(Screening)		Date of signing the ICF, with 00:00 added as timepart	First DB treatment administration datetime – 1 min
Double-Blind (DB) Treatment	Daily PE	First administration datetime of DB treatment	Start of DB post-daily PE subperiod – 1 min
	Post-daily PE	Date of switch to post-daily PE + 1 day with 00:00 added as timepart	Min(Week 5 visit date if no treatment extension or last visit date of treatment extension period with 23:59 added as timepart, early termination visit date with 23:59 added as timepart, first administration datetime of OL treatment – 1 min)
	Daily PE	First administration datetime of OL treatment	Start of OL post-daily PE subperiod – 1 min

CONFIDENTIAL

Open-label (OL) Treatment	Post-daily PE	Date of switch to post-daily PE + 1 day with 00:00 added as timepart	Min(Week 5 visit date if no treatment extension or last visit date of treatment extension period, early termination visit date) with 23:59 added as timepart
(Follow-up)		End of treatment period + 1 min	Trial termination date, with 23:59 added as timepart

Note that the last analysis period in case of early termination will always be ended by the trial termination date.

The 'overall treatment period' corresponds with the treatment analysis phase and covers both the DB treatment analysis period and the OL treatment analysis period. Note that only subjects who experience a relapse or exacerbation will have an OL treatment analysis period. For these subjects, the overall treatment period starts at start of DB treatment period and ends at end of OL treatment period. For subjects with no switch to open-label caplacizumab, the overall treatment period starts at start of DB treatment period and ends at end of DB treatment period.

The 'overall study period' covers both the treatment analysis phase and the follow-up analysis phase.

